2.2.2.1 Theory of Planned Behavior as underlying theory

TPB is a theory founded in the field of social psychology and is best suited to describe volitional behaviours especially health-related behaviours (Ajzen 1991; Godin and Kok 1996). TPB posits that a behaviour is influenced by attitude towards the behaviour, perceived subjective social norm towards the behaviour and perceived behavioural control towards the behaviour and is mediated by the intention to act. Attitude towards the behaviour is how one evaluate the advantages or disadvantages of performing a behaviour. Subjective social norm is the social expectations of a behaviour perceived by individual. Perceived behavioural control is personal perception about the difficulty and capability to perform a behaviour. Ajzen (1991) further revealed that perceived behavioural control has a direct effect to the behaviour when the a given behaviour having less

volitional control. Perceived behaviour control could reflect both external (such as time and money) and internal factors (such as skill and information), and this is similar to the self-efficacy construct conceptualized by Bandura (1977). Thus, the level of perceived behavioural control of an individual will determine the persistence of a given behaviour over time in the face of obstacles and setbacks. For better illustration of the value of TPB in explaining the behaviour of this study, medication-taking behaviour is influenced by attitude, perceived social norm and perceived behavioural control over the MA and all three factors are mediated by the intention towards MA while perceived behavioural control has also direct effect towards the behaviour. A recent systematic review and meta-analysis on the use of TPB in the studies about adherence will the treatment of chronic illness, further approve the feasibility of the TPB in the current study (Rich et al 2015). The TPB was found to account for 32.92% of the variance in intention and 9.18% of the variance in behaviour and all the relationship between variables were found to be consistent with the original hypotheses of the TPB.

2.2.2.2 Information-Motivation-Behavioral Skill Model as supporting theory

The IMB had been studied extensively among patients affected with Tuberculosis (Munro et al 2007) and HIV (Fisher et al 2006) who acquired to adhere to long-term medication to achieve clinical outcome. It had also been used to study the medication-taking behaviour and self-care behaviour among T2DM patients (Mayberry and Osborn 2014; Meunier et al. 2016).

IMB is a simple and latest behavioural model which have high predictive value on long-term medication adherence (Munro et al. 2007). The IMB posits that to achieve behavioural change, one should have adequate information, motivation and behavioural skills. In the context of MA, firstly a patient should have sufficient knowledge about his/her medical condition and medication.

Secondly, patient needs to be motivated to adhere, which include personal and social motivation. Lastly, one should have appropriate skills to carry out the task. Hence the researchers intend to adapt it as supporting theory for this study by putting adherence information as moderating factor between intention to adhere and actual medication adhering behaviour. Such hypothesis is supported by the fact that adherence information has direct effect on MA as posits by IMB.

2.2 Objectives of the study

This study aims to investigate the effectiveness of the SGBI “KYM-TIFH” in improving MA among Malay patients with underlying T2DM in the Sarawak State of Malaysia. Based on the two main research questions, three specific objectives of this study are:

- 1) to measure the effectiveness of the KYM-TIFH in improving medication adherence among Malay patients with underlying T2DM.
- 2) to test the predictive capacity of the integrated model in explaining the MA among Malay patients with underlying T2DM.
- 3) to measure the impact of the KYM-TIFH on the psychosocial variables of MA.

The conceptual framework that integrates TPB and IMB constructs to measure the effectiveness of the KYM-TIFH is illustrated in Figure 5.

[figure not shown]

Figure 5: Conceptual framework of the study (TPB constructs are in black colour while IMB construct is in red colour)

2.3 Hypotheses

Based on the first specific objective, two hypotheses to be tested are:

H1a: There is significant difference of medication adherence level among participants before and after the intervention.

H1b: There is significant difference of medication adherence level after the intervention between participants from intervention group and control group.

Based on the second specific objective, six hypotheses to be tested are:

H2a: There is a significant relationship between attitude to adherence and intention to adhere.

H2b: There is a significant relationship between subjective norm to adherence and intention to adhere.

H2c: There is a significant relationship between perceived behavior control to adherence and intention to adhere.

H2d: There is a significant relationship between perceived behavior control to adherence and medication adherence.

H2e: There is a significant relationship between intention to adherence and medication adherence.

H2f: There is a moderating effect by adherence information between intention to adhere and medication adherence.

Based on the third specific objective, five hypotheses to be tested are:

H3a: There is significant difference of attitude to adhere after the intervention between participants from intervention group and control group.

H3b: There is significant difference of subjective norm to adhere after the intervention between participants from intervention group and control group.

H3c: There is significant difference of perceived behavioural control to adhere after the intervention between participants from intervention group and control group.

H3d: There is significant difference of intention to adhere after the intervention between participants from intervention group and control group.

H3e: There is significant difference of adherence information after the intervention between participants from intervention group and control group.

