1.4 Problem statements

A current systematic review by Odgers-Jewell et al (2017) revealed that little had been done to investigate the effectiveness of group based education in improving medication adherence among T2DM patients. This concur with the comprehensive review on interventions to improve medication adherence by Conn & Ruppap (2017), as the researchers conclude that there is an urgent need in evaluating the interventions to improve medication adherence that employ group-based approach.

While MTAC had been proven to be effective in improving the MA among T2DM patients (PSD 2013; Conn & Ruppap 2017), the evidence on the effectiveness of the group based educational approach (KYM-TIFH in specific) in promoting medication adherence among T2DM patients remain lacking. Furthermore, the current measurement on the effectiveness of the campaign is the increment of the awareness level of public towards proper use of medicines (NSUM 2008, NSUM 2012) without measuring the impact of the campaign on actual behaviour.

Besides aforementioned, Malay ethnic was found to be the main contributor to the prevalence of poor MA (PSD 2013) due to forgetfulness (75.3%) and reluctant to take prescribed medications (43.8%). Facing the high prevalence of poor MA among Malay patients, an effective and efficient approach which could engage more patients within shorter period of times to improve the medication adherence problems is highly preferred (Odgers-Jewell 2017). Hence, all the problem statements addressed above lead to the necessity of conducting this study, which aims to investigate the effectiveness of the SGBI “KYM-TIFH” in improving MA among Malay patients with T2DM.

CHAPTER 2: LITERATURE REVIEW

Overview

The researchers of this study intend to further address the problem statements mentioned above and to justify the necessity of conducting this study based on two main research questions: (1) Is measuring the effectiveness of the SGBI KYM-TIFH among Malay T2DM patients a necessity? (2) What is the gap on the effectiveness of group-based intervention in improving medication adherence among T2DM patients?

2.1 First research question: Is measuring the effectiveness of the SGBI-TIFH among Malay T2DM patients a necessity?

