2.4 Operational definitions

(1) Medication adherence: Medication adherence is defined as the level of patients in complying with the medications prescribed by healthcare providers. Such level of compliance is measured through a self-reported scale MALMAS (Chung et al. 2015) which had been validated among T2DM patients in Malaysia.

(2) T2DM Malay patients: Type 2 Diabetes Mellitus Malay patients of this study refers to all the patients who are prescribed with oral anti-hyperglycaemic agents (OHA) and obtain their medications supply from the pharmacy department of KS-HC and PJ-HC during the study period. Such T2DM patients whose identity card show their religion as Islam, will be considered as Malay T2DM patients for this study.

(3) Cluster Randomized Controlled Trial: Cluster Randomized Controlled Trial refers to the study design employed by this study with accordance to the Recommendations for Intervention Trials “SPIRIT” (Chan et al. 2013) and will be reported in accordance to the Consolidated Standards of Reporting Trials (CONSORT) Statements with extension to cluster randomized trials (Campbell et al. 2012).

(4) Structured group based intervention: The structured group based intervention of this study refers to the program “Know Your Medicine – Take it for Health” which was formulated and employed by the Pharmaceutical Services Division of Sarawak State Health Department in late 2016 under the national campaign “Know Your Medicine” to promote medication adherence among T2DM Malay patients. The official name of the intervention is “Kenali Ubat Anda –

Ambillah untuk Kesehatan” in Malay language or “Know Your Medicine – Take it for Health” in English with abbreviation KYM-TIFH.

(5) Effectiveness: The effectiveness of this study refers to the improvement of medication adherence level among T2DM Malay patients before and after the SGBI with such improvement having significant difference as compared to the results in control group. Furthermore, the effectiveness of the SGBI will be complemented by the qualitative data through focus group discussion and semi-structured interview.

(6) Complications: The complications in this study refers to the diabetes-related complications including retinopathy, nephropathy, diabetic foot problems, ischemic heart disease and stroke that had been diagnosed by doctors and were documented in patients’ medical records during the period of study.

Chapter 3: Research Methodology

Overview

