3.3 Study setting- the study sites or clusters

The selected study sites that would enable the researchers of this study to engage with the targeted population are Petra Jaya Health Clinic (PJ-HC) and Kota Samarahan Health Clinic (KS-HC) that are funded by Malaysian government. Residents who reside at Petra Jaya and Kota Samarahan are able to access to quality healthcare services at the Health Clinic Petra Jaya (PJ-HC) and Health Clinic Kota Samarahan (KS-HC) respectively. Both clinics have medical specialist, medical officers, pharmacists, nurses and other allied health professionals to run the services such as emergency unit, out-patient unit, maternal & child clinic, pathology unit, X-Ray unit, disabled children development unit, counselling service unit and diabetes unit (Borneo Post Online 2014; Chew et al. 2017). Patients who suffered from T2DM can be diagnosed and get continuous consultations, medications and monitoring of the disease at the clinics. Nevertheless, both clinics will be run by a pharmacist who is specifically trained to run a diabetic MTAC (i.e. DMTAC) who shall also be referred to as a pharmacist in-charge of the DMTAC. He/she shall address any medication-related problems encountered by the patients in order to ensure that they will become adherent towards their complex multiple-medication treatment regimens. Only patients who deemed to have problems with adhering their medications will be referred by doctors to attend DMTAC. However, due to constraint in manpower, each diabetic pharmacist would only able to cater certain number of patients referred. Thus, the KYM-TIFH was designed with an aim to complement rather than competing the existing efforts.

With the aim to recruit suitable participants that could yield highly generalizable data to the studied population, PJ-HC and KS-HC are chosen as the study sites to recruit respondents and collect data. Moreover, the KS-HC had been included as one of the KYM-TIFH campaign site on 17-21 July 2017 while PJ-HC will be on 24-28 July 2017. Thus, the researchers incorporate this

study during the period of KYM-TIFH campaign by obtaining prior approval and financial support from Head of Department of the Sarawak Pharmaceutical Services Division.

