3.8.1 Intervention mapping and message design

The KYM-TIFH employed psychosocial, educational and behavioral approach. It was designed based on the application of multiple behavior change theories and persuasion theory as recommended by Slater (1999). The cross-theoretical framework for the message design of intervention as recommended by Slater (1999) involved theories such as Transtheoretical Model (TTM) (Prochaska & Velicer 1997), Theory of Reasoned Action (TRA) (Ajzen & Fishbein 1980), Protection Motivation Theory (PMT) (Rogers 1975), Elaboration-Likelihood Model (ELM) (Petty and Cacioppo 1986) and Social Cognitive Theory (SCT) (Bandura 1992) as in Table 2. Nonetheless, the intervention embrace the philosophy of patients' empowerment, which had found to be effective in engaging patients to produce behavioral change among diabetes patients (Anderson 1995; Anderson et al 1995). Hence, the facilitators are trained to employ non-didactic

approach in facilitating the and eliciting the learning among the group members. The intervention mapping as illustrated in Figure 8, depicts the appropriate outcomes for audiences at each stage of change for use in designing campaign objectives following the recommendations by Slater (1999).

Figure 8: Intervention mapping and the outcomes for audiences at each stage of change

Based on the intervention mapping and message design strategies using cross-theoretical approach, the intervention message delivery strategies are depicted in Table 3. After the completion of the program, participants will be asked to fill in the questionnaire with the assistance of four facilitators (APPENDIX D). A briefing on how to answer the questionnaire will be given by main facilitator and all facilitators are allowed to answer any questions raised by respondents related to the questionnaire. However, they are not allowed to answer on behalf of the respondents. After the completion of the questionnaire, they will be informed about the subsequent follow up measurement after one, three and six month. After that, they will be dismissed and having usual care provided by the health clinic as before without any changes.

Table 2: Message design strategies using cross-theoretical framework approach (adopted from Slater 1999)

Pre-contemplation to contemplation	Contemplation to Preparation	Preparation to action	Action to maintenance

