3.8.2 Content of Control Group

Participants who are assigned to control group, they will be asked to fill in the questionnaire with the assistance of four facilitators (APPENDIX D) right away without any intended input given to participants. A briefing on how to answer the questionnaire will be given by main facilitator and all facilitators are allowed to answer any questions raised by respondents related to the questionnaire. However, they are not allowed to answer on behalf of the respondents. After the completion of the questionnaire, they will be informed about the subsequent follow up measurement after one, three and six month. After that, they will be dismissed and having usual care provided by the health clinic as before without any changes.

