3.9 Outcome measurement

Primary outcome:

A validated 8-item Malay version of Medication Adherence Scale (MALMAS) will be employed to assess the level of medication adherence among Sarawak patients (Chung et al. 2015). All the items were translated into Bahasa Malaysia and were back translated to English by a group of four experienced language lecturers from University of Malaysia Sarawak.

Secondary outcome:

The psychosocial variables of Theory of Planned Behaviour and adherence information variable from IMB will be employed as secondary outcome of this study. The sources of the items to measure all the variables in conceptual framework are depicted in Table 4.

Paper-based questionnaires will be distributed to the targeted patients by trained enumerators during the group based intervention. Prior to answering the survey, subjects will be briefed about the structure of the questionnaire and how to answer the questions by main facilitator. Any enquiries raised by the respondents will be explained by facilitators.

Table 4: Instrument for the study

Variable	No. of items	Measuring scale	Adopted from
Adherence information	6	5 points Likert scale	McPherson et al. 2008
Attitude to adhere	5	5 points Likert scale	Farmer et al. 2006

Subjective Norm to adhere	6	5 points Likert scale	Farmer et al. 2006
Perceived Behavioural Control to adhere	11	5 points Likert scale	Fernandez et al. 2008
Intention to adhere	3	5 points Likert scale	Vissman et al 2013
Medication adherence	8	1-7 items are measured with binomial answers which are “yes” or “no”; the last item is measured with 5 points Likert scale	Chung et al. 2015
Demographic	15	(1) enrolled with diabetic MTAC; (2) numbers of medications, one or more than one; (3) frequency of the medications, a once-daily dose or more frequent; (4) age; (5) gender; (6) highest education level; (7) monthly household income; (8) employment status; (9) having complications; (10) taking traditional complementary and alternative medicines; (11) residential area, urban or rural; (12) living condition, having social support or stay individually; (13) undergone diabetic education by diabetic nurse; (14) newly diagnosed or established T2DM; (15) concurrent diseases	

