3.11.2 Data analysis for first objective

The first objective of this study is to measure the effectiveness of the intervention in improving medication adherence. Descriptive statistics will be used to present the results on the level of medication adherence before and after the intervention. Mann-Whitney U test will be used to examine the change of patients between adherent patients (MALMAS > 6) and non-adherent patients (MALMAS < 6) before and after the intervention within same group. In terms of inter-group comparison for the medication adherence level (adherent vs non-adherent) before and after the intervention, Wilcoxon signed-rank will be executed.

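### H1a, an uncontrolled before/after test, stands as its own effectiveness hypothesis under objective 1, although section 2.4(5) requires a difference from control

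*Protocol*

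**What the plan says.** - Protocol section 2.2 sets objective 1 as measuring the effectiveness of the programme in improving adherence. Section 2.3 attaches two hypotheses to it without ranking them. The first is "H1a: There is significant difference of medication adherence level among participants before and after the intervention". H1b compares the intervention and control groups after the intervention.
- Section 3.11.2 tests the change between "adherent patients (MALMAS > 6) and non-adherent patients (MALMAS < 6) before and after the intervention within same group". The comparison between groups is a separate sentence.
- Section 2.4(5) defines effectiveness as improvement from before to after, "with such improvement having significant difference as compared to the results in control group".
- Section 3.4.1 admits only patients with MALMAS below 6, scored at what section 3.5 calls the T0 screening.
- A session-day score is also possible as the before value. Table 3 schedules a questionnaire before the programme begins, control participants "fill in the questionnaire with the assistance of four facilitators (APPENDIX D) right away" (3.8.2), and 3.9 states: "Paper-based questionnaires will be distributed to the targeted patients by trained enumerators during the group based intervention".
- After the session both arms are described as "having usual care provided by the health clinic as before without any changes" (3.8.1, repeated in 3.8.2).

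**The concern.** H1a covers only the first half of the definition in 2.4(5). It cannot separate the programme from time, repeated questioning or usual care, whichever MALMAS score counts as before. The protocol itself describes usual care that could raise adherence. On the diabetic adherence clinic, section 3.3 says: "Only patients who deemed to have problems with adhering their medications will be referred by doctors to attend DMTAC". Section 1.4 says: "While MTAC had been proven to be effective in improving the MA among T2DM patients".

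If the screening score is the before value, selection adds a second problem. Everyone starts non-adherent, so the category in 3.11.2 can move only upward, and regression to the mean raises the average score. A trial of an ineffective programme could then report one of its two effectiveness hypotheses as supported.

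**Working it through.** **The plan's own figure.** Section 3.7 takes SD 1.8, a difference of 1, power 0.90 and a 1:1 ratio. Two-sided α = 0.05 is assumed, since the section states α only for objective 2.

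n per group = 2(1.960 + 1.282)² × 1.8² / 1² ≈ 68.1, rounded up to 69. The stated 69 is reproduced. It is a between-group calculation, so it fits H1b and not H1a.

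**Model for H1a.** Scores are normal with SD 1.8, there is no programme effect, and entry requires a screening score below 6. Not in the protocol and therefore assumed: unselected mean μ from 5 to 7 and test-retest correlation r from 0.6 to 0.8. The exact McNemar test stands in for a paired test on the two categories of 3.11.2. A score of exactly 6, which falls in neither category, is counted as not having crossed.

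**Screening score as before.**

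1. Expected rise = (1 − r)(μ − E[X | X < 6]), where E[X | X < 6] = μ − 1.8 φ(a)/Φ(a) and a = (6 − μ)/1.8. For μ = 6 and r = 0.7: E = 6 − 1.8 × 0.3989/0.5 = 4.56, and the rise is 0.3 × 1.44 = 0.43. Over the range it is 0.17 (μ 5, r 0.8) to 0.85 (μ 7, r 0.6).
2. Chance of crossing above 6 at follow-up: 12.3% to 43.2% for a continuous score. For whole points (entry at 5 or less, adherent at 7 or more) it is 3.8% to 25.6%.
3. No downward move is possible, so K upward moves give p = 2 × 0.5^K. K = 5 gives 0.0625 and K = 6 gives 0.031. The test rejects when K is 6 or more.
4. P(K ≥ 6):

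| Scoring | n | μ 5 to 7 | μ 4 |
|---|---|---|---|
| Continuous | 69 | 87–100% | 26–57% |
| Whole points | 69 | 5–100% | 0–5% |
| Whole points | 155 (70% of 221) | 54–100% | 6–55% |

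The low whole-point cells at n = 69 are 5% and 26% (μ 5, r 0.8 and 0.7) and 35% (μ 6, r 0.8).

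5. On the score rather than the category, a paired t test at n = 69 rejects in 24% to over 99% (continuous, μ 5 to 7). The between-arm test on the post score stays at 4.4% to 5.8%. With these t tests, H1a is significant while the between-arm test is not in 23% to 95% of trials.

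**Session-day score as before** (three equally correlated measurements, selection on the first, n = 69, μ 5 to 7). The drift is an assumed upward shift common to both arms.

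| Common drift | McNemar, continuous | McNemar, whole points |
|---|---|---|
| 0 | 0–3% | at or below nominal |
| 0.25 points | about 6–16% | about 1–9% |
| 0.5 points | about 24–56% | about 12–37% |

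A paired t test on the score gives more, 25–45% and 73–95% for the two drifts, but 3.11.2 analyses the category, so the McNemar rows are the relevant ones.

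**Testing within each arm does not help.** With no effect, each arm rejects with the same chance p. Significant in the intervention arm but not in the control arm then has chance p(1 − p), which reaches 0.5 × 0.5 = 25%.

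**The case against.** The strongest reply is that 2.4(5) already contains the safeguard. H1a and H1b roughly match its two halves, and requiring both to be significant gives at most about 5% error. The protocol nowhere says that H1a alone would be declared effectiveness, and the sample size rests only on the between-group difference. This stands, and it limits the weight of the point. It does not remove it: neither 2.3 nor 3.11.2 states a joint requirement, and H1a remains a stand-alone hypothesis under the effectiveness objective.

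The sizes are also open to challenge, rightly. The mean, the correlation and the drift are assumptions. Usual care is said to continue unchanged, section 3.3 notes that adherence-clinic capacity is limited by manpower, and no passage documents a rise after the session. The large rates need the screening score as the before value. What does not depend on any of this is that H1a has no control term.

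A reader might infer that regression to the mean also biases H1b. It does not: both randomised arms are selected in the same way, and the between-arm error stays near 5%. A reader might also count the unnamed baseline as an error. That is not supported, because Figure 11 is not shown and an SAP could name the baseline.

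**Conclusion.** The point holds in a limited form. Sections 2.3 and 3.11.2 treat an uncontrolled before/after test as an effectiveness hypothesis, and 2.4(5) does not accept such a change on its own. With no programme effect, H1a rejects in about 5% to 100% of trials on the category at n = 69 if the screening score is the before value (SD 1.8 from the protocol; mean 5 to 7 and correlation 0.6 to 0.8 assumed). With a session-day score it is nominal without drift, and roughly 6–16% or 24–56% with an assumed common drift of 0.25 or 0.5 points (continuous score), lower with whole-point scoring.

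It is tempting to read these rates as the trial's chance of a false effectiveness claim. The documents do not support that, because 2.4(5) bars H1a alone from establishing effectiveness. The exposure is a significant H1a being reported as support for objective 1 when H1b is not supported. Weight: minor to moderate.

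**What to change.** 1. In 2.3, make H1a descriptive, and change the within-group sentence in 3.11.2 to match: show the change from baseline in both arms, without a test of effectiveness.
2. Rest objective 1 on the between-arm comparison. Reword H1b, which now compares post-intervention levels while 2.4(5) speaks of improvement differing from control. Suitable wording is intervention versus control in post-intervention MALMAS, adjusted for the same named baseline MALMAS score in both arms. With that adjustment, analysing the post score or the change gives the same group difference, so this also expresses a difference in improvement. The adjustment serves precision and agreement with 2.4(5); it is not needed to remove bias.

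Cost: one within-group test is dropped. A baseline MALMAS is already collected, and the 69 per group already rest on the between-group difference, so data and sample size do not change.
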